Diastolic function should be categorized as normal, mild dysfunction (impaired relaxation pattern), moderate dysfunction (pseudonormal filling), or severe dysfunction (restrictive filling) per the 2009 American Society of Echocardiography recommendations.⁴⁵

B.5 Core Lab Analysis

Protocol-required echocardiograms will be sent to the Echo Core lab for assessment: the data generated by the Echo Core Lab will be the primary data used for analysis and reporting. Received echocardiograms will be logged in and analyzed by the Echo Core Lab according to their procedures determined for this study. Qualitative assessment of valvular regurgitation will be performed using the criteria described in Sections B.4.4 through B.4.6.

The Echo Core Lab will report the following variables:

- Heart rate
- Aortic annulus diameter (pre-implant only)
- Left ventricular outflow tract (LVOT) diameter in mid systole
- Max aortic/prosthetic valve velocity (V_2) by CW Doppler
- Aortic valve velocity time integral (VTI) by CW Doppler
- Mean gradient across aortic valve (MGV_2) by CW Doppler
- LVOT VTI by PW Doppler
- Right ventricular outflow tract (RVOT) diameter(post-implant; if aortic regurgitation > mild by visual estimate)
- RVOT VTI (post-implant; if aortic regurgitation > mild by visual estimate)
- Grade of aortic/prosthetic transvalvular regurgitation (post-implant only)
- Grade of aortic/prosthetic paravalvular regurgitation (post-implant only)
- Grade of prosthetic total (transvalvular plus paravalvular) regurgitation (post-implant only)
- Grade of mitral regurgitation
- Grade of tricuspid regurgitation
- Max tricuspid regurgitant (TR) jet velocity (if TR is present)
- Left ventricular internal dimension at end diastole
- Left ventricular internal dimension at end systole
- Interventricular septal thickness at end diastole
- Left ventricular posterior wall thickness at end diastole
- Left atrial diameter (anterior-posterior linear dimension) at systole
- Left ventricular ejection fraction by visual estimate
- Grade of diastolic dysfunction (if present)

In addition, the following variables will be derived by the central database from the appropriate measurements reported by the Echo Core Lab:

- Peak Pressure Gradient (Peak ΔP) Across the Aortic Valve in mmHg
$$\text{Peak } \Delta P = 4 \times (V_2^2)$$

Where: V_2 is the peak velocity across the prosthesis in m/sec
- Aortic Valve Area (AVA) in cm^2

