3.7.1.3. Endpoint Definition

Device success, defined in accordance with the VARC-2 composite endpoint of device success:

- Absence of procedural mortality, and
- Correct positioning of a single prosthetic heart valve into the proper anatomical location, and
- Intended performance of the prosthetic heart valve, defined as the absence of patient-prosthesis-mismatch and mean aortic valve gradient less than 20 mmHg (or peak velocity < 3 m/sec), and absence of moderate or severe prosthetic valve regurgitation.

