3.7.1.4. Data Collection and Analysis Methods

The components of device success will be determined as follows:

- No death event occurs within 30 days post-procedure, or on or before the discharge date (if the discharge date is longer than 30 days post-procedure);
- In the implant CRF, the answer to “Was a single Evolut R deployed in the proper anatomical location?” should be “YES”;
- The criteria for ECHO will be based on the ECHO Core Lab Data for the time interval “Discharge”:
 - Absence of patient-prosthesis-mismatch
 - For subjects with BMI < 30 kg/m², index effective orifice area (EOAi) > 0.85 cm²/m²
 - For subjects with BMI ≥ 30 kg/m², index effective orifice area (EOAi) > 0.70 cm²/m²
 - BMI = weight(kg)/(height (m))², where weight and height are recorded on the ECHO CORE LAB form
 - Mean aortic gradient < 20 mmHg or peak velocity < 3 m/sec;
 - Absence of moderate or severe prosthetic valve regurgitation. Total Aortic Prosthetic Regurgitation on the ECHO CORE LAB form not equal to moderate or severe.

All of the above components must be satisfied to count as a device success. If any of the above components fails, the endpoint will be counted as a failure.

For the overall device success rate, the numerator will be the number of subjects whose procedures result in device success as described above, and the denominator will be the number of subjects whose device success results are not missing (either success or failure). Note that this analysis excludes those subjects with a missing response to any of the above five components (eg, the field “Post-implant Severity of Total Aortic Regurgitation”=“Unable to Assess” or “Not Recorded”, missing mean aortic gradient, or missing peak velocity, etc.) and without a “NO” response to any

of the components. In addition to the device success rate, the 95% C.I. will also be provided. This objective will be analyzed for the implanted analysis set defined in section 3.4.

3.7.2.Secondary Objective #2 (Efficacy) - Hemodynamic Performance

This objective is to characterize the hemodynamic performance at 24 hours to 7 days (discharge) and 1 year post procedure.

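### SAP 3.7.1.4 lets either gradient or velocity meet the component, yet lists either one missing as a missing component, so the device-success denominator is ambiguous and known successes may be dropped

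*SAP*

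**What the plan says.** SAP 3.7.1.3 defines intended valve performance with an either/or limit: "mean aortic valve gradient less than 20 mmHg (or peak velocity < 3 m/sec"). SAP 3.7.1.4 repeats it for the core-lab data as "Mean aortic gradient < 20 mmHg or peak velocity < 3 m/sec". Protocol 2.2.2 has the same either/or form.

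SAP 3.7.1.4 then sets the counting rules:

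- **Failure:** "If any of the above components fails, the endpoint will be counted as a failure".
- **Denominator:** "the denominator will be the number of subjects whose device success results are not missing (either success or failure").
- **Exclusion:** "this analysis excludes those subjects with a missing response to any of the above five components", limited to subjects with no failed component ("and without a “NO” response to any" of them).
- **Examples of missingness**, in a bracketed list that is marked as illustrative: an unassessable regurgitation grade, and "missing mean aortic gradient, or missing peak velocity".

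The objective is descriptive. It reports a rate with a two-sided 95% confidence interval, with no test (SAP 3.7.1.1) and no sample-size calculation (SAP 3.7.1.2). It is analysed in the implanted set.

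**The concern.** An either/or criterion is settled once one of its two measures is within its limit; the other value adds nothing. Listing each absent value, on its own, as a missing component treats the criterion as if both values were needed. Take a subject with a mean gradient of 9 mmHg, no peak velocity and the other four components satisfied. The endpoint definition makes this a success, while the exclusion examples make it missing.

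The loss is not symmetric. A subject with the same gap who fails on death, position, mismatch or regurgitation has a NO and stays in as a failure. What is at stake is the size of the denominator and a possible downward pull on the first secondary efficacy endpoint. Two programmers could also obtain different results from the same text.

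**Working it through.** The plan states no device-success rate and no missingness rate, so there is no figure to reproduce. The check has two parts.

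**1. Logic.** The SAP's count of five components is reached as: no death, single valve in the proper place, no mismatch, gradient/velocity, no moderate or severe regurgitation. Gradient and velocity must therefore be one component; taken separately there would be six. Let gradient and velocity each be *meets*, *fails* or *missing*, and let the other four components together be YES, NO or missing. That gives 3 × 3 × 3 = 27 patterns. Classify each under the literal note (either value missing makes the component missing) and under either/or logic (YES if one value meets its limit, NO if both are recorded and both fail, otherwise missing). Exactly two patterns differ:

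| Gradient | Velocity | Other four | Literal note | Either/or logic |
|---|---|---|---|---|
| meets | missing | YES | excluded | success |
| missing | meets | YES | excluded | success |

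No failure changes status.

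**2. Size.** All inputs are assumptions:

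- *s*, the true success rate: 70–90%.
- *m*, the share of subjects with exactly one of the two values, unrelated to outcome: 1–5%.
- *g*, the share of failures that fail on gradient/velocity only. With one value missing, these subjects have no determinable NO, so they are excluded too.
- In a true success with one value, the recorded value is within its limit.

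Literal rate = (1−m)s / [(1−m)s + (1−s)(1−mg)]

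Either/or rate = s / [s + (1−s)(1−mg)]

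With g = 0, the extreme case, the either/or rate equals s and the literal rate is:

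| s | m = 1% | m = 5% |
|---|---|---|
| 70% | 0.693/0.993 = 69.8% (−0.2) | 0.665/0.965 = 68.9% (−1.1) |
| 80% | 0.792/0.992 = 79.8% (−0.2) | 0.760/0.960 = 79.2% (−0.8) |
| 90% | 0.891/0.991 = 89.9% (−0.1) | 0.855/0.955 = 89.5% (−0.5) |

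At s = 80% and m = 5%, that is 0.05 × 800 = 40 successes dropped per 1000.

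With g above 0, at s = 80% and m = 5%:

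| g | Literal rate | Either/or rate |
|---|---|---|
| 0.25 | 0.76/(0.76 + 0.1975) = 79.4% | 0.80/(0.80 + 0.1975) = 80.2% |
| 0.50 | 0.76/(0.76 + 0.195) = 79.6% | 0.80/(0.80 + 0.195) = 80.4% |
| 1 | 0.76/(0.76 + 0.19) = 80.0% | 0.80/(0.80 + 0.19) = 80.8% |

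The two errors are about equal at g = 0.5. Below that, either/or logic is closer to the truth; above it, the literal note is.

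For scale, the 95% half-width at 80% with n = 1000 is 1.96 × √(0.8 × 0.2/1000), about 2.5 points.

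**The case against.** The strongest reply is that the SAP already does the right thing. Its operative rule speaks of five components, its denominator takes everyone whose result is known, and the disputed words are only examples of how a component might come to be missing. A programmer following the count of five and the stated *or* would keep the subject with a gradient of 9 mmHg. This reading is available, so the documents do not support a reader's inference that the plan definitely discards successes. But the examples name each value separately and point the other way. The text needs one rule.

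The second reply is that hardly anyone is affected, and this largely stands. Protocol Appendix B.5 lists peak velocity and "Mean gradient across aortic valve" as separate reported variables, but that shows only separate fields. Under Appendix B.4.3, one continuous-wave Doppler curve supplies the peak velocity and, once traced, both the mean gradient and the valve VTI. The effective orifice area needs that VTI (Appendix B.5). If the curve was not traced, mismatch is missing as well, and a subject with no NO elsewhere is excluded under either reading. The rules differ only when the VTI is there but exactly one of gradient and velocity is not.

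Third, the downward shift is not guaranteed at its full size, because failures on this component alone can be dropped too. This is correct, and the working allows for it through *g*.

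Fourth, nothing inferential depends on the endpoint, and SAP 3.3 already requires the number analysed to be reported. Both are true. They limit the importance of the point, but a reported count does not tell the reader which rule produced it.

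**Conclusion.** The point holds as an internal inconsistency in SAP 3.7.1.4 with a probably small effect. Followed literally, the exclusion note removes subjects whom the endpoint definition makes successes, and this tends to lower the rate. At a true rate of 80% with 1–5% of subjects having one value, the shift is at most about −0.2 to −0.8 points. It shrinks as more failures are on gradient/velocity alone, and disappears if all are. These sizes rest on assumed rates and on missingness unrelated to outcome. The shared Doppler curve suggests that few subjects are affected.

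A reader might infer a material bias in the efficacy result. The documents do not support that: they give no missingness rate, the shift in the main 80% example is well inside the interval's half-width of about 2.5 points, and the objective carries no test, alpha or sample size. Nor should a reader infer that either/or logic is free of bias, since one recorded value can establish YES but never NO. Clarifying the text is worthwhile and minor.

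**What to change.** In SAP 3.7.1.4, define the gradient/velocity component as:

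- YES if at least one recorded value meets its limit;
- NO if both values are recorded and neither meets its limit;
- MISSING otherwise.

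In the exclusion examples, replace "missing mean aortic gradient, or missing peak velocity" with: neither recorded value meets its limit and at least one is missing.

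Report how many subjects have one failing value with the other missing and are excluded for that reason. Add a sensitivity analysis that counts them as failures. This addresses the small upward bias that either/or logic can leave (80.2% against 80% in the example with g = 0.25).

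The cost is a sentence or two in the SAP, one line of derivation code and one extra table row. No new data are needed, nothing is imputed in the main analysis, and the limits themselves are unchanged. The change should be made before the analysis is run.

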3.7.2.1. Hypothesis and/or Parameters to Be Estimated

The objective is descriptive and no statistical hypothesis test will be performed.

3.7.2.2. Sample Size Consideration

There was no sample size calculation for this objective.

3.7.2.3. Endpoint Definition

The following hemodynamic metrics as measured by transthoracic echocardiography (TTE) and assessed by an independent core laboratory will be summarized:

- Mean prosthetic valve gradient
- Effective orifice area
- Degree of prosthetic valve regurgitation (transvalvular, paravalvular, and total).

3.7.2.4. Data Collection and Analysis Methods

Echo core lab data will be used. This objective will be analyzed for the implanted analysis set.

3.7.3.Secondary Objective #3 and #4 (Safety) - Event Rate of the VARC-2 Combined Safety Endpoint and Individual Safety Components at 30 Days

These two objectives are to characterize the safety event rates at 30 days based on the VARC-2 Combined Safety Endpoint and individual safety components.

3.7.3.1. Hypothesis and/or Parameters to Be Estimated

The objectives are descriptive and no statistical hypothesis test will be performed.

3.7.3.2. Sample Size Consideration

There was no sample size calculation for these objectives.

3.7.3.3. Endpoint Definition

The VARC-2 Combined Safety Endpoint at 30 days includes the following components:

- All-cause mortality
- All stroke (disabling and non-disabling)
- Life-threatening bleeding
- Acute kidney injury: stage 2 or 3 (including renal replacement therapy)
- Coronary artery obstruction requiring intervention
- Major vascular complication
- Valve-related dysfunction requiring repeat procedure (BAV, TAVI, or SAVR)

3.7.3.4. Data Collection and Analysis Methods

The CEC codes for the VARC-2 Combined Safety Endpoint:

- All-cause mortality (CEC Death Form)
- All stroke (disabling and non-disabling) (CEC: 102 to 107)
- Life-threatening bleeding (CEC: 110)
- Acute kidney injury: stage 2 or 3 (including renal replacement therapy) (CEC: 114 to 115)

- Coronary artery obstruction requiring intervention (CEC: 152)
- Major vascular complication (CEC: 120 to 127)
- Valve-related dysfunction requiring repeat procedure (BAV, TAVI, or SAVR)
 - Catheter intervention to repair or replace Evolut R
 - Surgery intervention on Evolut R

As described in section 3.5, a Kaplan-Meier analysis will be performed for the VARC-2 Combined Safety Endpoint at 30 days post-procedure and for each individual component. These objectives will be analyzed for the safety analysis set defined in section 3.4.

3.7.4. Secondary Objective #5 (Safety) - Event Rate of New Permanent Pacemaker Implant at 30 Days

This objective is to characterize the event rate of new permanent pacemaker implant at 30 days.

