2.2.3 Secondary Safety Endpoints

4. Early Safety composite endpoint at 30 days post procedure, defined according to the VARC-2 guidelines³², defined as any of the following components:
 - All-cause mortality
 - All stroke (*disabling and non-disabling*)

ⁱ Time window for Echo assessment

- Life-threatening bleeding
 - Acute kidney injury: stage 2 or 3 (*including renal replacement therapy*)
 - Coronary artery obstruction requiring intervention
 - Major vascular complication
 - Valve-related dysfunction requiring repeat procedure (*BAV, TAVI, or SAVR*)
5. Event rates of the individual components of the VARC-2 composite Early Safety endpoint³² at 30 days post procedure
 6. Rate of new permanent pacemaker implant at 30 days post procedure

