5.7.2 Recording and reporting of Adverse Events

Investigators are required to report all serious adverse events (SAE) and all VARC 2 Adverse Events (AE) regardless of seriousness observed in the study subjects from their point of enrollment until completion of follow-up. The list of VARC 2 Adverse Events is provided in table 7. The event definitions and event code list can be found in Appendix E and G, respectively.

Table 7. List of VARC 2 Adverse Events

Event Type
All-cause Mortality
Myocardial Infarction
Stroke and TIA
Thrombo-embolic events (eg, stroke)
Bleeding
Vascular Access Site and Access-Related Complications
Acute Kidney Injury
New and/or worsened conduction disturbances
Repeat procedure (BAV, TAVI, or SAVR)
Hospitalizations for valve-related symptoms or worsening congestive heart failure
TAV in TAV deployment
Conversion to open surgery
Unplanned use of cardiopulmonary bypass (CPB)
Coronary artery obstruction
Ventricular septal perforation
Mitral valve apparatus damage or dysfunction
Cardiac tamponade
Prosthetic valve endocarditis
Prosthetic valve thrombosis
Valve migration
Valve embolization
Ectopic valve deployment
Stent fracture

The VARC-2 document provides standardization of endpoint definitions for studies evaluating the use of TAVI. This study follows VARC-2 to allow for improved comparability and interpretability of study results. Due to the nature and regulatory strategy of this study, the scope of Adverse Event reporting in this study has been limited to reporting of all SAE's and all VARC 2 Adverse Events (AE) regardless of seriousness. This is a deviation from ISO14155:2011.

These Adverse Events, documented in the subject's medical record will be reported to Medtronic on an Adverse Event e-CRF as described in this section.

For all reportable AEs, investigators should assess and document the following information on the Adverse Event e-CRF:

- Date of onset or first observation
- Date site became aware of the event
- AE code number
- Description of the event
- Seriousness of the event
- Causal relationship of the event to the Evolut R™ TAV
- Causal relationship of the event to the Enveo R™ DCS
- Causal relationship of the event to the implant procedure
- Treatment required
- Outcome or status of the event

Refer to section 5.7.6 for emergency contact details for reporting events and device deficiencies, especially for immediate reporting.

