5.7.7 Clinical Events Committee

A Clinical Events Committee (CEC) will provide independent medical review and adjudication of adverse event data. The CEC will adjudicate at least all deaths and safety endpoint events reported by the investigators. Further adverse events could be reviewed and adjudicated upon request of the Sponsor. The CEC will follow the recommendations of VARC-2³⁴ for classifying adverse events that relate to clinical safety endpoints

The CEC members will be free from bias towards the study and will be independent from both the study and investigators and Medtronic. The committee will consist of at least 3 independent experts (non-Medtronic employed physicians) with expertise relevant to the study. This may include experience in the areas of:

- Cardiac surgery
- Interventional cardiology
- Neurology
- Electrophysiology

A CEC charter will be developed and approved by Medtronic.

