APPENDIX E. DEFINITIONS: SAFETY ENDPOINTS AND EFFICACY EVENTS

Definitions of adverse events to be evaluated as clinical safety endpoints, other TAVI-related complications, and efficacy events are provided in Sections E.1, E.2, and E.3, respectively. Site investigators and the CEC will code events according to these definitions, using the associated code list provided in appendix G, Event Code List.

E.1 Safety Endpoint Definitions³²

Mortality	
Cardiovascular mortality	
Any of the following criteria:
 
 1) Death due to proximate cardiac cause (eg, myocardial infarction, cardiac tamponade, worsening heart failure) 2) Death caused by non-coronary vascular conditions such as neurological events, pulmonary embolism, ruptured aortic aneurysm, dissecting aneurysm, or other vascular disease 3) All procedure-related deaths, including those related to a complication of the procedure or treatment for a complication of the procedure 4) All valve-related deaths including structural or nonstructural valve dysfunction or other valve-related adverse events 5) Sudden or unwitnessed death 6) Death of unknown cause
Non-cardiovascular mortality	Any death in which the primary cause of death is clearly related to another condition (eg, trauma, cancer, suicide).

Myocardial Infarction	
Periprocedural MI (≤72 h after the index procedure)	
New ischemic symptoms (e.g, chest pain or shortness of breath), or new ischemic signs (e.g, ventricular arrhythmias, new or worsening heart failure, new ST-segment changes, hemodynamic instability, new pathological Q-waves in at least 2 contiguous leads, imaging evidence of new loss of viable myocardium or new wall motion abnormality) AND
 
Elevated cardiac biomarkers (preferable CK-MB) within 72 h after the index procedure, consisting of at least 1 sample post procedure with a peak value exceeding 15x as the upper reference limit for troponin or 5x for CK-MB. If cardiac biomarkers are increased at baseline (>99th percentile), a further increase in at least 50% post procedure is required AND the peak value must exceed the previously stated limit.

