Minor vascular complication	
 1) Access site or access-related vascular injury (dissection, stenosis, perforation, rupture, arterio-venous fistula, pseudoaneurysms, hematomas, percutaneous closure device failure) not leading to death, life-threatening or major bleeding*, visceral ischemia, or neurological impairment OR 2) Distal embolization treated with embolectomy and/or thrombectomy and not resulting in amputation or irreversible end-organ damage OR 3) Any unplanned endovascular stenting or unplanned surgical intervention not meeting the criteria for a major vascular complication OR 4) Vascular repair or the need for vascular repair (via surgery, ultrasound-guided compression, transcatheter embolization, or stent-graft)
Percutaneous closure device failure	Failure of a closure device to achieve hemostasis at the arteriotomy site leading to alternative treatment (other than manual compression or adjunctive endovascular ballooning)

*Refer to VARC bleeding definitions

VALVE DYSFUNCTION REQUIRING REPEAT PROCEDURE
Any valve dysfunction that requires repeat procedure (e.g. balloon valvuloplasty, TAVI, or surgical AVR)

Note: Repeat procedures are reported on the appropriate e-CRF (Surgical Intervention or Catheter Reintervention)

E.2 Other TAVI Related Complications

Complication	Definition
Conversion to open surgery	Conversion to open sternotomy during the TAVI procedure secondary to any procedure-related complications
Unplanned use of cardiopulmonary bypass	Unplanned use of CPB for hemodynamic support at any time during the TAVI procedure
Coronary artery obstruction	Angiographic or echocardiographic evidence of a new, partial or complete, obstruction of a coronary ostium, either by the Evolut R prosthesis itself, the native leaflets, calcifications, or dissection, occurring during or after the TAVI procedure.
Ventricular septal perforation	Angiographic or echocardiographic evidence of a new septal perforation during or after the TAVI procedure
Mitral valve apparatus damage or dysfunction	Angiographic or echocardiographic evidence of new damage (chordae, papillary muscle, or leaflet) to the mitral valve apparatus or dysfunction (e.g. restrictions due to the Evolut R) of the mitral valve during or after the TAVI procedure
Cardiac tamponade	Evidence of new pericardial effusion associated with hemodynamic instability and clearly related to the TAVI procedure

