APPENDIX G. EVENT CODE LIST

Myocardial Infarction

- 100 Peri-procedural myocardial infarction
- 101 Spontaneous myocardial infarction

Stroke and TIA

- 102 Disabling stroke: ischemic
- 103 Disabling stroke: hemorrhagic
- 104 Disabling stroke: undetermined origin
- 105 Non-disabling stroke: ischemic
- 106 Non-disabling stroke: hemorrhagic
- 107 Non-disabling stroke: undetermined origin
- 108 Transient ischemic attack

Bleeding Complications

- 110 Life threatening or disabling bleeding event
- 111 Major bleeding event
- 112 Minor bleeding event

Acute Kidney Injury

- 113 Acute kidney injury: stage 1
- 114 Acute kidney injury: stage 2
- 115 Acute kidney injury: stage 3

Vascular Access and Access Site Complications

Major

- 120 Major vascular complication: aortic dissection, aortic rupture, LV perforation, or new apical aneurysm/pseudoaneurysm
- 121 Major vascular complication: access site or access site-related vascular injury (dissection, stenosis, perforation, etc)
- 122 Major vascular complication: distal embolization from vascular source
- 123 Unplanned endovascular or surgical intervention
- 124 New ipsilateral lower extremity ischemia
- 125 Surgery for access site-related nerve injury
- 126 Permanent access site-related nerve injury
- 127 Other major vascular complication

Minor

- 130 Minor vascular complication: access site or access site-related vascular injury
- 131 Minor vascular complication: distal embolization from vascular source
- 132 Unplanned endovascular stenting or unplanned surgical intervention not meeting criteria for major complication
- 133 Vascular repair or need for vascular repair
- 134 Other minor vascular access site complication
- 140 Failure of closure device leading to alternative treatment

Other TAVI-Related Complications

- 150 Conversion to open surgery
- 151 Unplanned use of CPB
- 152 Coronary artery obstruction
- 153 Ventricular septal perforation
- 154 Mitral valve apparatus damage or dysfunction
- 155 Cardiac tamponade
- 156 Prosthetic valve thrombosis
- 157 Valve migration
- 158 Valve embolization
- 159 Ectopic valve deployment
- 160 TAV in TAV deployment
- 161 Major hemolysis
- 162 Minor hemolysis
- 163 Prosthetic valve endocarditis: definite
- 164 Prosthetic valve endocarditis: possible
- 165 Major frame fracture
- 166 Minor frame fracture
- 167 Other TAVI-related complication

Conduction Disturbances and Arrhythmias

- 170 Atrio-ventricular block, 1°
- 171 Atrio-ventricular block, 2°

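### The SAP derives the coronary component of the 30-day safety endpoint from CEC code 152, which has no intervention criterion, and names no data item to apply one

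*SAP*

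**What the plan says.** Protocol 2.2.3 lists "Coronary artery obstruction requiring intervention" as one component of the VARC-2 Early Safety composite at 30 days (secondary endpoint 4). The individual components are also reported separately (secondary endpoint 5). SAP 3.7.3.3 repeats the component with the same limit.

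SAP 3.7.3.4 then lists the CEC codes for the composite. The entry for this component is "Coronary artery obstruction requiring intervention (CEC: 152". No second field, form or condition is given.

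In the Protocol's Appendix G the code reads "152 Coronary artery obstruction". Appendix E.2 defines the event as "Angiographic or echocardiographic evidence of a new, partial or complete, obstruction of a coronary ostium", caused by the prosthesis, native leaflets, calcification or dissection, during or after the procedure. Treatment is not mentioned. Appendix E also states that "Site investigators and the CEC will code events according to these definitions".

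On what reaches the committee, Protocol 5.7.7 says "The CEC will adjudicate at least all deaths and safety endpoint events reported by the investigators" and adds "Further adverse events could be reviewed and adjudicated upon request of the Sponsor".

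**The concern.** The endpoint has two conditions: an obstruction, and a need for intervention. The code in the SAP records only the first. A program that selects code 152 would count a partial obstruction seen on imaging and left untreated, and that event is outside the endpoint as both documents define it.

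At stake is the accuracy of one separately reported component and, to a lesser degree, of the composite. Protocol 5.7.2 says that the study follows VARC-2 so that its results can be compared with those of other studies. A component wider than its label works against that aim.

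**Working it through.** The plan states no figure to reproduce here, so the check is mainly a comparison of sections.

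**1. Does each source in SAP 3.7.3.4 carry its component's limit?** (Codes from Appendix G.)

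| Component | Source in SAP 3.7.3.4 | Limit carried by the source? |
|---|---|---|
| Death | CEC death form | Yes |
| Stroke | 102 to 107 | Yes; TIA is 108 and left out |
| Life-threatening bleeding | 110 | Yes; major and minor bleeding are 111 and 112 |
| Kidney injury stage 2 or 3 | 114 to 115 | Yes; stage 1 is 113 |
| Coronary obstruction needing intervention | 152 | **No**; treated and untreated share the code |
| Major vascular complication | 120 to 127 | Yes; minor ones are 130 to 134 |
| Valve dysfunction needing a repeat procedure | Catheter or surgical intervention on the valve | Yes; the interventions are named |

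The coronary line is the only one whose source is wider than its component.

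**2. Does the code system separate events by intervention elsewhere?** Yes. Hemolysis is split on that ground into codes 161 (major) and 162 (minor). Need for intervention is also one of the criteria that separate frame fracture codes 165 and 166. Code 152 is not split.

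**3. Can untreated obstructions enter the data?** At site level, yes. Table 7 in Protocol 5.7.2 lists coronary artery obstruction without a treatment condition, and Table 7 events are reportable whether or not they are serious.

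**4. Would the CEC code them 152?** This is not settled.
- Against: Protocol 5.7.7 requires adjudication of deaths and safety endpoint events, and an untreated obstruction is not an endpoint event.
- For: Protocol 2.4 and SAP section 2 use a wider phrase, covering adverse events related to safety endpoints. Appendix E has the CEC code by its definitions, and 152 is the only code specific to coronary obstruction.

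**5. Size per subject.** Take about 1000 subjects (the planned number implanted; the safety set also includes attempted implants) and little censoring before day 30, which is an assumption. One wrongly counted subject adds about 1/1000 = 0.1 percentage point to the 30-day component rate. The composite rises by the same amount only if that subject has no other composite event by day 30.

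**6. Total.** With k wrongly counted subjects the component rises by about k × 0.1 percentage point. The documents give neither the frequency of code 152 nor the untreated share, so k is unknown. For scale only, an assumed 2 to 10 coded subjects per 1000 with an untreated share of 0 to 50% gives k from 2 × 0 = 0 to 10 × 0.5 = 5, or 0 to 0.5 percentage points.

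**The case against.** The best defence is that the SAP line does state the rule. The words requiring intervention stand next to the code, directly after the same definition in SAP 3.7.3.3. A careful programmer would treat the words as the condition and the code as the place to look. The CEC also follows VARC-2 when it classifies events related to safety endpoints. Its charter and the case report forms, which are separate documents, are where an intervention item would normally sit.

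Much of this stands. A reader might infer that the SAP drops the qualifier or redefines the endpoint; it does neither, because it repeats the words. A reader might also infer that the study has no means of separating treated from untreated events. The documents do not show that, since the charter and forms may provide one. Nor do they show that untreated obstructions will be counted, because CEC coding of such events is unsettled.

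The defence does not supply the missing source. In that list the words name the component and the bracketed code is the derivation. The instruction to follow VARC-2 does not change the definition of code 152 or say where the qualifier is recorded, and SAP 3.7.3.4 does not point to a charter or form item for it.

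**Conclusion.** The point holds as a specification gap of low severity. The code mapping in SAP 3.7.3.4 is wider than the endpoint in Protocol 2.2.3 and SAP 3.7.3.3, and if it is programmed on the code alone, any untreated obstruction that the CEC codes 152 is counted.

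The direction is upward only, so the gap cannot make the device look safer. The total effect cannot be estimated from the documents and may be zero. The range in the working rests on assumed inputs and is not evidence of material inflation. SAP 3.7.3.1 makes these objectives descriptive with no test, and neither the primary mortality test nor the sample size is touched.

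**What to change.** In SAP 3.7.3.4, derive the component as CEC code 152 **and** a CEC-confirmed intervention (yes/no) for that obstruction. If the adjudication form or charter already has such an item, cite it; if not, add it. A CEC item fits the rule in SAP section 2 that safety endpoint results rest on CEC adjudications.

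The adverse event form has a site-reported entry, "Treatment required" (Protocol 5.7.2). Use it only as supporting information for the adjudication. The documents do not show what entries it allows, and it may record treatment that is not an intervention.

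The cost is one SAP line, at most one yes/no item for the CEC, and a re-check of any events already coded 152. The protocol and Appendix G need no change.
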